## 1. INTRODUCTION

### 1.1. Mechanism of Action/Indication

PF-06252616 is a humanized monoclonal antibody which binds and neutralizes myostatin, also known as growth differentiation factor 8 (GDF-8), a negative regulator of muscle mass.

The proposed indication is the treatment of Duchenne muscular dystrophy (DMD).

Protocol B5161004 is an open-label extension (OLE) to Protocol B5161002 and will provide an assessment of the long term safety, efficacy, PD and PK of IV dosing of PF-06252616 in boys with DMD.

### 1.2. Background and Rationale

#### 1.2.1. Myostatin Role in Muscle Regulation

Myostatin or GDF-8 is a member of the transforming growth factor- $\beta$  (TGF $\beta$ ) superfamily of secreted differentiation factors (McNally, 2004). The role of GDF-8 as a negative regulator of muscle fiber growth and mass is well conserved between zebrafish, dogs, cattle, mice and humans. The effect of inhibiting GDF-8 has been best studied in skeletal muscle; knockout GDF-8  $-/-$  mice possess muscles that are 100% to 200% larger than wild type controls due to a combination of muscle fiber hyperplasia and hypertrophy (McPherron et al, 1997). Despite having increased skeletal muscle and decreased fat, the GDF-8 knockout mice appear to be normal and healthy. Consistent with its role in mice, genetic loss of myostatin is associated with increased muscle mass in many different species (McNally, 2004). One case of a human has been reported with a homozygous mutation of the GDF-8 gene, associated with an absence of GDF-8 protein, in which the boy was found to have increased muscle strength and, by age 4, no apparent untoward health effects (Schuelke et al, 2004). Pharmacologic inhibition of GDF-8 activity in rodents resulted in increased muscle mass and improved muscle function in both normal and dystrophic animals (Bradley et al, 2008). Given its effect on skeletal muscle and the absence of abnormality in knockout mice, GDF-8 represents an attractive target for diseases associated with muscle loss.

#### 1.2.2. Duchenne Muscular Dystrophy

DMD is the most frequently inherited neuromuscular disease, and predominantly affects boys. It is an X-linked muscular dystrophy caused by a mutation at Xp21 in the gene coding for the protein dystrophin (Bushby et al, 2010; Manzur et al, 2008) which is absent from the muscle of boys with DMD. DMD is the most severe of all muscular dystrophies and is characterized by skeletal and cardiac muscle degeneration. Boys with DMD are phenotypically unremarkable at birth; onset of symptoms usually occurs around two to three years of age. Most boys lose the ability to walk between the ages of 10 and 14 (Lamperti & Moggio, 2010). Progressive cardiac problems manifest in the second decade.

There is no approved treatment that can stop or reverse the progression of DMD. Glucocorticoid therapy, although not specifically approved for use in DMD, is the only pharmacotherapy that has been demonstrated to ameliorate symptoms in patients with DMD,

irrespective of underlying mutation, and is currently the standard of care. Although glucocorticoids may improve muscle strength for a period of time and delay the loss of ambulation, (Mendell et al, 1989; Bonifati et al, 2000), chronic use is associated with well-known adverse events such as weight gain and broad hypothalamic-pituitary-adrenal axis effects which eventually lead to the discontinuation of treatment, often in the teenage years.

Additional disease management consists primarily of supportive care which ranges from physical therapy to maximize function and minimize muscle contractures, to orthotics, tendon release surgery (which provides temporary benefit as contractures will redevelop), use of wheel chair (usually by age 12), surgical correction of scoliosis and use of respiratory care including various forms of assisted ventilation (including tracheotomy). Respiratory infections may be treated with antibiotics. Death from pneumonia or cardiac involvement in late teens or early twenties is commonly observed in these patients (Manzur et al, 2008).

### **1.2.3. PF-06252616**

PF-06252616, also referred to as Anti-Myostatin, is a humanized recombinant antibody immunoglobulin G1 (IgG1) that neutralizes GDF-8 (myostatin). PF-06252616 was developed by humanization of a mouse monoclonal antibody, designated mRK35, generated by immunizing GDF-8 knockout mice with recombinant GDF-8 and isolating monoclonal antibodies by splenic fusion using standard hybridoma methodology. The substitution of specific amino acid residues in the Fc region of PF-06252616 has reduced the effector functions of the molecule. The humanized recombinant antibody has a human kappa constant domain and a human IgG1 constant domain with 3 mutations to reduce potential effector function. PF-06252616 investigational drug product is supplied as a lyophilized sterile powder in a single use glass vial. The vials will be reconstituted with sterile water for injection (SWFI). The reconstituted PF-06252616 drug product is clear to slightly opalescent and colorless to slightly colored in appearance.

### **1.3. Clinical Experience with PF-06252616**

The clinical program for PF-06252616 was initiated in June 2012 with a Phase 1 first-in-human (FIH), randomized, double-blind (sponsor and pharmacist unblinded), placebo-controlled study (B5161001) evaluating the safety, tolerability, pharmacokinetic, pharmacodynamic, and pharmacologic (anabolic) effects of escalating single doses of PF-06252616 in healthy adult subjects. The study is complete with 73 subjects enrolled at a single site. Single doses of 1, 3, 10, 20, and 40 mg/kg administered by the intravenous (IV) route and 3 mg/kg administered by the subcutaneous route, or placebo were studied. In addition, a repeat IV administration of PF-06252616 10 mg/kg at 2 week intervals over a 28-day treatment period was investigated. Safety was demonstrated at all dose levels and there were no dose-related trends in frequency of reported treatment-emergent adverse events (TEAEs).

The Protocol B5161002 is the first-in-patient (FIP) study with PF-06252616. This Phase 2 randomized, 2-period, double blind, placebo-controlled, multiple-ascending dose study aims to provide initial clinical assessment of the safety, efficacy, PK, and PD of PF-06252616

following repeat IV doses in ambulatory boys with DMD. Additionally, it aims to demonstrate the efficacy of treatment over 3 escalated IV dose levels of PF-06252616 based on an observed mean change from baseline on function 4SC as compared to placebo following 49 weeks of treatment. The study is ongoing and plans to enroll approximately 105 eligible subjects who will be randomly assigned to 1 of 3 sequence groups and receive placebo or investigational product PF-06252616 at 3 escalating dose levels of 5 mg/kg IV, 20 mg/kg IV, and 40 mg/kg IV administered every 4 weeks for approximately 96 weeks (2 treatment periods of approximately 48 weeks each).

Complete information for this compound may be found in the Single Reference Safety Document (SRSD), which for this study is the [Investigator's Brochure \(IB\)](#).

#### **1.4. Rationale for Dosage Selection and Method of Administration**

The dose for each subject will be based on their individual maximum tolerated dose (MTD) up to 40 mg/kg from Study B5161002. This study will use the same route and frequency of administration as Study B5161002. IV was chosen as the route of administration for B5161002 to support the large dose that will be required to obtain the targeted GDF-8 coverage. The frequency of administration was chosen as 4 weeks to achieve targeted GDF-8 coverage but also to reduce the burden on subject travel to study sites.

#### **1.5. Study Design Rationale**

This is an OLE of the B5161002 study designed primarily to evaluate the long-term safety of PF-06252616 as well as to collect data regarding maintenance of effect up to 4 years.

#### **1.6. Anticipated Risks and Safety Monitoring**

Anticipated risks are based on clinical and toxicology data which can be found in the IB.

##### **1.6.1. Hepatic Injury**

CCI

In DMD, serum alanine transaminase (ALT) and aspartate transaminase (AST) elevation related to muscle pathology is common and well described ([McMillan et al, 2011](#)). Therefore the utility of these enzymes as markers of hepatocellular injury is limited. Glutamate dehydrogenase (GLDH) has been identified as a biomarker of liver injury that is independent of muscle damage. Using a validated assay, GLDH will be evaluated to provide additional information regarding liver function.

Abnormal values for serum ALT or AST concurrent with abnormal elevations in total bilirubin that meet the criteria for Hy's law and in the absence of other causes of liver injury are considered potential cases of drug-induced liver injury (potential Hy's law cases) and should always be considered important medical events. Subject data meeting these criteria will be referred to the external data monitoring committee (E-DMC) for review. In addition, Liver MRI will be obtained according to the [Schedule of Activities](#) to monitor for safety by

quantifying iron accumulation. The E-DMC will include a Hepatic Expert to review any cases of potential liver toxicity.

#### **1.6.2. Gastric Erosion and Haemorrhage**

CCI

Given the use of systemic glucocorticoids in the DMD population, there is a risk of increased incidence of gastric erosion and haemorrhage. Study subjects will therefore be asked specifically to report symptoms that may be associated with such pathology. Monitoring of haemoglobin, haematocrit and fecal occult blood will be performed.

#### **1.6.3. CCI Sexual Development**

CCI

Given the target population of DMD pre-pubertal boys, this effect needs to be monitored. Tanner staging and testicular volume will be used to monitor pubertal development, in addition to the measurement of sex hormone levels and bone age with a wrist and hand X-ray assessment. Should boys reach sexually maturity during the trial as indicated by a Tanner Stage V rating, monitoring will no longer be mandatory.

#### **1.6.4. Bone Metabolism**

CCI

is therefore appropriate to examine BMD in the DMD population. CCI effect on BMD – especially in those treated with glucocorticoids – would clearly be CCI DXA will be used to monitor for changes in BMD.

#### **1.6.5. Cardiac**

CCI

However, based on literature regarding the biology of GDF-8 and GDF-11 and their potential modulation of cardiomyocyte and cardiac function, combined with the known cardiac dysfunction in the target population of DMD boys, it is appropriate to focus on the potential for an interaction between the drug and the underlying disease state. The ongoing Phase 2 Study (B5161002) includes monitoring with 12-lead electrocardiogram (ECG) for rhythm or morphological change, cardiac Troponin I for cardiac muscle tissue injury, and cardiac MRI with gadolinium (or echocardiography if cardiac MRI is not available at the site) to evaluate left ventricular

ejection fraction (LVEF). Subjects will remain on the same imaging modality to assure consistency in safety measure from Study B5161002 through Study B5161004. Additional cardiac parameters (eg, left ventricular wall thickness, cardiac strain, and fibrosis) may be collected during cardiac MR imaging for exploratory analyses. Abnormal values for each of these measures have been reported in DMD, even in patients under the age of 10. In light of the variability of findings during the natural history of the disease, no pre-specified stopping rules have been defined. Cardiac monitoring will continue in this study as outlined in the [Schedule of Activities](#).

#### **1.6.6. Radiation**

The possible risks related to subjects undergoing evaluation with DXA and x-ray for bone age includes the risk of radiation exposure. The average effective dose of radiation received for a single DXA scan or hand x-ray for bone age may vary due to the instrument and the subject's body. Annual assessments include a whole body DXA scan, a DXA spine scan and a single x-ray image of the hand and wrist. The expected annual radiation dose resulting from these scans for a subject participating in this study should not exceed 0.15 mSv per year. This is less than 1 month of natural background radiation which is approximately 0.25 mSv per month (Environment, Health & Safety (EHS) Radiation Risk; [Blake et al, 2006](#)).

#### **1.6.7. Other Risks**

Possible risks related to the administration of the study drug and/or as a consequence to phlebotomy may include hematoma or bruising.

#### **1.6.8. Other Safety Monitoring**

Additional safety monitoring will include the parameters of adverse events (AEs), physical examination, vital signs, and clinical laboratory parameters (including urinalysis, hematology, gamma-glutamyl transferase [GGT], GLDH, prothrombin time/activated partial thromboplastin time [PT/aPTT], creatine kinase, amylase, and chemistry) and Columbia Suicide Severity Rating Scale (C-SSRS) (see [Clinical Outcomes Assessment manual](#)). Laboratory monitoring will also be performed to detect ADA and NAb.

### **1.7. Summary of Risk Benefit**

In view of the initial clinical evidence of safety and the monitorable nature of key nonclinical toxicological findings, data support an acceptable risk profile for PF-06252616 in the current study and support a favorable benefit-risk profile in the indication of DMD. Authorities will be kept informed of any additional data (eg, results from clinical studies) which may affect the assessment of the risk/benefit ratio for PF-06252616.

## **2. STUDY OBJECTIVES AND ENDPOINTS**

### **2.1. Objectives**

#### **2.1.1. Primary Objective**

To evaluate the long-term safety of IV dosing of PF-06252616 in boys with DMD.

### **2.1.2. Secondary Objectives**

- To evaluate the long-term efficacy of PF-06252616 using functional assessments and strength.
- To assess the PK and immunogenicity of PF-06252616.

### **2.1.3. Exploratory Objectives**

- To evaluate PD markers that may be informative in demonstrating the pharmacologic effect of PF-06252616.
- To evaluate the long-term functional health effects of PF-06252616 on Parent-report and Adolescent self-report scores on the PODCI.
- To assess the long-term effects of PF-06252616 on HRQL and healthcare resource utilization (HRU) in boys with DMD.
- To evaluate the long-term effects of PF-06252616 on caregiver burden, HRQL and work productivity and activity impairment.
- To collect exploratory biomarker samples for bio-banking.

## **2.2. Endpoints**

### **2.2.1. Primary endpoints**

#### **2.2.1.1. Safety**

- Incidence and/or rate of intolerance or dose limiting treatment related AEs following up to 4 years of treatment.
- Incidence and/or rate, severity and causal relationship of TEAEs and withdrawals due to TEAEs following up to 4 years of treatment.
- Incidence and magnitude of abnormal laboratory findings (clinical laboratory tests: hematology, chemistry, GGT, GLDH, PT, aPTT, creatine kinase, amylase, serum ferritin, serum iron, total iron binding capacity (TIBC), % transferrin saturation. Hormones: luteinizing hormone [LH], follicle stimulating hormone [FSH], thyroxine [T4], thyroid stimulating hormone [TSH]. Fecal occult blood, cardiac Troponin I and urinalysis) following up to 4 years of treatment.
- Abnormal and clinically relevant changes in liver MRI and physical examinations (including nose and throat mucosal exam and Tanner stage and Testicular Volume), weight, vitals, electrocardiogram (ECG), LVEF measured by cardiac MRI (or echocardiogram), bone mineral density by DXA, x-ray (hand and wrist for bone age evaluation) and C-SSRS.

## **2.2.2. Secondary endpoints**

### **2.2.2.1. Efficacy**

- Mean change from baseline following up to 4 years of treatment in the following functional assessment tests PFTs (to include FVC, FEV1 and PEFR), 4SC, NSAA, PUL, ROM and 6MWD.
- Mean change from baseline in muscle strength measured by myometry following up to 4 years of treatment.

### **2.2.2.2. PK and Immunogenicity**

Trough serum PF-06252616 concentrations for all subjects receiving active drug.

- Incidence of ADA and NAb.

## **2.2.3. Exploratory Endpoints**

### **2.2.3.1. PD**

To evaluate change from baseline of Lean Body Mass (LBM) determined via whole body DXA after up to 4 years of treatment.

### **2.2.3.2. Clinical Outcome Assessments**

- To evaluate the long-term functional health effects of PF-06252616:
  - Changes from baseline in the Pediatric Outcomes Data Collection Instrument (PODCI) Parent-report and Adolescent self-report scores.
  - Change from baseline in the EuroQol 5 Dimensions 3 Levels (EQ-5D-3L) Health Questionnaire.
  - Change from baseline in the EuroQol 5 Dimensions - Youth (EQ-5D-Y) Health Questionnaire.
  - Change from baseline in Healthcare Resource Utilization (HRU) questionnaire.
  - Change from baseline in Zarit Burden Interview (ZBI).
  - Change from baseline in the Work Productivity and Activity Impairment. Questionnaire adapted for caregiving (WPAI:CG) in the percent work time missed, percent impairment while working, percent overall work impairment, and percent activity impairment due to a child's Duchenne muscular dystrophy.
  - Pooled or exploratory analyses, if conducted, utilizing the biobanked exploratory genomic and biomarker samples will be documented in the statistical analysis plan.

### **3. STUDY DESIGN**

#### **3.1. Study Overview**

This is a Phase 2 OLE to protocol B5161002 and will provide an assessment of the long term safety, efficacy, PD and PK of IV dosing of PF-06252616 in boys with DMD.

The individual dose level selected for each subject will be based on the maximum tolerated dose (MTD) from the parent study B5161002. However, dose levels may be adjusted based on emerging safety or efficacy data from B5161002.

Subjects will be dosed with one of three PF-06252616 dose levels:

- 5 mg/kg
- 20 mg/kg
- 40 mg/kg

Approximately 105 eligible subjects will be assigned to receive an individualized MTD based on their tolerability profile/data from B5161002. No placebo comparator will be assessed. Consenting subjects who complete the B5161002 study will be invited to transition directly to the OLE study. Subjects' results from the B5161002 study may be used as screening data for the current study if the subject is enrolled within 42 days of Week 97 visit of B5161002, see [Schedule of Activities](#) and [Assessments](#) for details. If this window is exceeded, the sponsor and investigator will assess if the subject may still participate in this OLE study, and which, if any, assessments must be completed to confirm eligibility.

#### **3.2. Duration of Study and Subject Participation**

The OLE study is planned to be conducted over a period of 4 years. The end of the study will be the last visit of the last subject for purposes of closing out sites, informing the institutional review board/ethics committee (IRB/EC), and ceasing to send Council for International Organizations of Medical Sciences (CIOMS) reports.

Depending on when subjects begin the OLE study, their participation may be as long as 4 years. Subjects may be withdrawn from the OLE study should the parent study, B5161002 fail to meet its planned study objectives, is terminated early for other reasons (eg, sponsor decision) or the drug is commercialized.

Subjects will be administered monthly infusions of study drug as well as completion of safety and efficacy assessments as per the [Schedule of Activities](#).

In the case where subjects are traveling from a distance, local overnight accommodation will be offered.

### **3.3. Planned Number of Subjects**

Approximately 105 subjects will participate in multiple centers and countries worldwide.

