### **Study Design**

Approximately 105 eligible subjects will be assigned to receive an individualized maximum tolerated dose based on their tolerability profile/data from B5161002. No placebo comparator will be assessed. Consenting subjects who complete the B5161002 study will be

invited to transition directly to the OLE study. Subjects' results from the B5161002 study may be used as screening data for the current study.

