### **4.1. Inclusion Criteria**

Subject and caregiver eligibility should be reviewed and documented by an appropriate member of the investigator's study team before subjects are included in the study.

Subjects must meet all of the following inclusion criteria to be eligible for enrollment into the study:

1. Subjects with Duchenne muscular dystrophy who enrolled and completed through Week 97 of Study B5161002.
2. Evidence of a personally signed and dated informed consent document (ICD) indicating that the subject's parent or legal guardian/caregiver has been informed of all pertinent aspects of the study. Subjects may be required to provide assent in compliance with local regulations and IRB requirements.
3. Subjects and their legal guardians/caregivers who are willing and able to comply with scheduled visits, treatment plan, laboratory tests, and other study procedures.
4. The following inclusion criteria will be assessed using data from the B5161002 study, and if data are unavailable, these assessments must be completed prior to enrollment:
  - a. Adequate hepatic function on screening laboratory assessments from the Week 97 visit.
  - b. GLDH  $\leq$  20 units/liter (2 x upper limit of normal [ULN]) from the Week 97 visit.
  - c. Iron content estimate on the liver MRI within the normal range as determined by R2\* value (R2\* $\leq$ 75 Hz at 1.5 T or R2\* $\leq$ 139 Hz at 3.0 T) from the Week 93 visit.

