Note: Results considered by the investigator to be transient and inconsistent with the subject's clinical condition may be repeated once during the screening period for confirmation of eligibility. The reason for repeating the assessment should be documented.

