It is important to note that some additional assessments may be required (eg, ambulatory status, PFTs to establish study baseline, medication history). As soon as these assessments are completed and a subject's eligibility has been confirmed, they may be enrolled into the study.

The PODCI child self-report (if eligible), EQ-5D-Y, EQ-5D-3L, ZBI, and HRU are new assessments not included in the parent study B5161002 and should be collected at screening and all subsequent visits outlined in the [Schedule of Activities](#). If a subject is unwilling to provide self-reported data they can still participate in the study.

If a subject becomes a screen failure for the current study, they will not be permitted to re-screen.

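### Should the extension's planned number of about 105 subjects be restated as a ceiling rather than as the number who will take part?

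*Protocol*

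**What the plan says.** Three places in the protocol give the size of this study as a plain number:

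- Protocol Summary, Study Design: "Approximately 105 eligible subjects will be assigned to receive an individualized maximum tolerated dose".
- Section 3.1: "Approximately 105 eligible subjects will be assigned to receive an individualized MTD".
- Section 3.3: "Approximately 105 subjects will participate in multiple centers and countries worldwide".

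Section 1.3 gives the same figure for the parent study, which is ongoing and "plans to enroll approximately 105 eligible subjects who will be randomly assigned to 1 of 3 sequence groups". Section 9.1 says that this study's size is limited by the parent's and sets the number enrolled there as a cap.

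Entry is restricted. Section 4.1 admits "Subjects with Duchenne muscular dystrophy who enrolled and completed through Week 97 of Study B5161002", and adds criteria on hepatic function, GLDH and liver iron. Section 3.1 says: "Consenting subjects who complete the B5161002 study will be invited to transition directly to the OLE study". Section 12.4 says that no recruitment effort is needed. On screening, Section 6 says: "If a subject becomes a screen failure for the current study, they will not be permitted to re-screen". The note to Section 4.2 softens this a little, since a result judged transient "may be repeated once during the screening period for confirmation of eligibility".

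**The concern.** Every step between parent enrolment and extension entry can only remove subjects: failure to reach Week 97, refusal of consent, a liver or MRI criterion not met, no suitable caregiver. Nothing adds subjects. If about 105 boys enter the parent study, about 105 entering the extension means that almost nobody is lost over roughly 96 weeks of dosing and a screening step. The words eligible and assigned, in the Summary and Section 3.1, also rule out reading 105 as the number invited.

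The primary objective is long-term safety, and 105 is the only planned head-count in the document. A reader who takes it as the expected safety sample would expect somewhat more ability to detect uncommon events than the study is likely to have.

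**Working it through.** **Inputs from the protocol.** Parent planned enrolment is about 105 (Section 1.3). The extension figure is about 105 (Summary, Sections 3.1 and 3.3). The cap is the number enrolled in the parent study (Section 9.1). The protocol gives no completion, consent or eligibility rate, so the rates below are assumptions.

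**Step 1. Reproduce the figure.** Entrants = parent enrolment × share completing Week 97 × share of completers who consent and are eligible. The stated number comes out only as 105 × 1.00 × 1.00 = 105, which is full carry-over. Without it, the parent would have to enrol more than planned: 105 / 0.95 = 110.5, so about 111 at 95% carry-over, or 105 / 0.90 = 116.7, so about 117 at 90%.

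**Step 2. Range of entrants under assumed rates.**

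- 95% complete, all of them enter: 105 × 0.95 × 1.00 = 99.8, about 100.
- 80% complete, 90% of them enter: 105 × 0.80 × 0.90 = 75.6, about 76.
- A harsher case, 70% and 80%: 105 × 0.70 × 0.80 = 58.8, about 59.

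**Step 3. What that does to the safety information.** With no events seen among N subjects, the exact one-sided 95% upper bound on the event rate is 1 − 0.05^(1/N). The chance of seeing at least one event of 1% incidence is 1 − 0.99^N.

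| N | Upper bound, zero events | Chance of at least one event at 1% |
|---|---|---|
| 105 | 2.8% | 65% |
| 100 | 3.0% | 63% |
| 76 | 3.9% | 53% |
| 59 | 5.0% | 45% |

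At the favourable end the difference is negligible. At the unfavourable end it can be seen, but which end applies cannot be told from the protocol.

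**Step 4. What uses 105.** Section 9 calls all analyses exploratory because the study is open label. Section 9.1 contains no power or precision calculation. Sections 9.2 to 9.4 plan summary statistics on whoever is observed, and Section 9.5 plans no interim analysis. None of these takes 105 as an input, so replacing it with 100, 76 or 59 alters no planned analysis and no rule.

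**Step 5. Is 105 really the ceiling?** Only approximately. The cap in Section 9.1 is the parent's actual enrolment, which was not final when this protocol was written. A few more or fewer than 105 could be enrolled there, and the cap would move with that number.

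**The case for a change.** The best argument for a change is that planned number and sample size belong in the protocol, and that the protocol states this one in a way that fits poorly with its own cap. The word approximately does not cure that. It qualifies the parent's figure as well, and it suggests variation either way, whereas the losses here run in one direction. The edit would be cheap: a qualifier in three places and a sentence of expected numbers in Section 9.1. Section 13.1 also ties the end of trial in an EU Member State to the number in the regulatory application, so an accurate figure has some administrative use.

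The textual part of this stands: Section 3.3, read alone, overstates the likely intake. The rest carries little weight. The sample-size section already states the limit, and the Summary and Section 3.1 give the consent and completion condition shortly after the number. Section 13.1 treats recruiting fewer than anticipated as a normal conclusion. A forecast of entrants would need rates that the protocol does not contain, and nothing planned would use the result. Nor would a corrected head-count give the expected exposure, because Section 3.2 leaves duration open: up to 4 years, with withdrawal possible if the parent study fails or stops early, or the drug is commercialized.

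**Conclusion.** The number is approximately a maximum, subject to the parent's actual enrolment, and three places word it as the number who will take part. That is a minor inconsistency of wording with Section 9.1, not an error of calculation or design. Under assumed overall carry-over of 72% (0.80 × 0.90) to 95%, the shortfall is about 5 to 29 subjects, and the zero-event bound moves from 2.8% to between 3.0% and 3.9%. The size of the shortfall rests wholly on those assumptions.

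No change to the plan is called for. Intake is whatever the parent study yields, the cap is stated where sample size is determined, the analyses are descriptive, and no conclusion depends on reaching 105. The report will use the actual number treated. Adding up to before the figure would be harmless tidying if the protocol were being amended for another reason, but it would not improve the design, conduct or analysis.
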